From recent meta-analysis, three dual-armed studies that compared embolization and conventional surgery groups and six single-armed case series were identified and analyzed. Hematoma recurrence rate was significantly lower in the embolization group compared to the conventional treatment group (2.1% vs 27.7%, OR .087, 95% CI .026-.292, $p<.001$, $I^2=0\%$), whereas surgical complication rates were similar between the two (2.1% vs 4.4%, OR 0.563, 95% CI 0.107-2.96, $p=.497$, $I^2=27.5\%$). Number of patients with mRS>2 in the embolization (12.5%) versus conventional treatment (9.1%) groups also showed no statistical difference ($p=.689$). A composite hematoma recurrence rate of 3.6% was found after summing the six-case series. Composite recurrence and complication rates in the embolization cohorts of the dual-armed studies as well as the case series were also lower than literature values for conventional surgical treatments. Since then, there has been one study with 60 embolizations showing a 90% success rate of avoiding subsequent surgery with no procedural-related complications.

Objective

Through the use of a prospective dual cohort, this study seeks to assess the safety and efficacy of middle meningeal artery embolization for subdural hematoma in addition to standard treatments, which include observation and surgical evacuation. Middle meningeal artery embolization has emerged recently as a minimally invasive and successful method of preventing re-accumulation of subdural hematoma, particularly for patients that are not obvious surgical candidates or those with recurrent or refractory hematomas. We will compare the outcomes of these two groups of patients who undergo middle meningeal artery embolization to matched historical controls from the past four years.

Specific Aim 1:

Determine the efficacy of middle meningeal artery embolization vs observation alone

The recurrence rate of patients that undergo the middle meningeal artery procedure will be compared to a number of medically managed patients that experience a clinically significant persistent or recurrent hematoma. This endpoint will be determined through a series of neurologic assessments and follow up imaging. Patients will be followed for 90 days.

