information gathered, time frame of participation, potential benefits, and risks of participation, including the risks of undergoing an interventional neuroradiology procedure. Treatment with middle meningeal artery embolization will be offered in addition to the standard surgical evacuation or observation by the physician in consideration of the patient's medical history and current condition. If patients are unable to provide informed consent, consent from the next of kin will be obtained in accordance with Missouri Statute Title XXVII, Section 431.064.

Patients will have as much time as they desire to think about the study, ask questions, and discuss with family. Any patient requiring emergent intervention or experiencing sudden neurologic deterioration is excluded from this study. The consent documentation contains a statement that consent is freely given, that the patient understands the potential risks and benefits of entering the study, and that the patient is free to withdraw from the study at any time. As the patient may experience a direct benefit from the study, the patient must initial yes/no to permission for future use of their data per policy. Patients who agree will then sign the IRB approved consent form prior to undergoing the procedure. The original signed consent will be maintained in a binder in a locked office. A copy will be given to the patient, with contact numbers if the patient has further questions or wishes to withdraw their consent. The expected duration of patient participation in the study is 90 days.

Based on a review of prior literature, we expect an effect size of 20% patients to meet the endpoint of recurrent or refractory subdural hematoma requiring surgery. With the addition of MMA embolization, we expect that only 5% of patients will meet this outcome. With equal numbers of patients in each arm, we estimate that 124 patients will be needed for a power of 80% using a two tailed alpha set at 0.5. In order to account for study dropout, we plan to study 200 patients who undergo MMA embolization. These patients will be compared to an additional 400 historical matched controls obtained via retrospective chart review from January 1st 2014 to December 31st 2018.

Inclusion/Exclusion Criteria

Must meet the following criteria for inclusion to undergo MMA embolization:

1. Patients 18 years or older undergoing treatment for a new diagnosis of chronic or acute subdural hematoma (cSDH)
or

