Statistical comparisons will be made for the number of patients that experience a recurrent or refractory subdural hematoma, as well as the number of patients in each group that require evacuation surgery after undergoing embolization, an indication that the embolization procedure failed. These primary endpoints will be compared with simple t-test. The secondary endpoint of the change in the size of the subdural hematoma on radiographic imaging will be analyzed by repeated measures ANOVA. Change in score on NIH Stroke Scale pre and post embolization will be compared to determine the functional outcome of the procedure. For a safety analysis, the rate of procedure-related complications between embolized patients and surgical controls will be compared by t-test. Rankin Score at the follow up intervals will be compared with a Chi Square analysis.

Safety Monitoring Plan

Research will be performed according to protocols approved by the Institutional Review Board at Washington University in St. Louis School of Medicine. An application to the IRB is currently pending.

Patients with subdural hematoma present with symptoms including confusion or altered mental status, decreased consciousness, weakness or numbness on one side of the body, headache, seizure, and difficulty with speech, swallowing, or walking.

During this study, assessment of medical history and physical examination will be performed at baseline and at stated follow up intervals to ascertain neurologic status, change in functional baseline, and occurrence of any AEs. Prior to interventional procedures, patients have coagulation tests performed to assess risk of bleeding. If the patient has an allergy to iodinated contrast, they will receive standard pre-medication. During the embolization procedure, patients undergo continuous vital sign monitoring and are assessed frequently by a dedicated, ACLS-certified procedural nurse. The patient will be monitored as an inpatient in the neuroICU or stepdown unit for a minimum of 24-48 hours after the procedure.

Adverse Events

An adverse event (AE) is any untoward medical occurrence in a subject during participation in the clinical study or with use of the experimental agent being studied. An adverse finding can include a sign, symptom, abnormal assessment (laboratory test value, vital signs, electrocardiogram finding, etc.), or any combination of these.

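### A t-test of unstated form on yes/no endpoints: a pooled interval would be 20% too wide at the planned rates, and Welch error on rare complications depends on an unstated control count

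*Combined protocol and SAP*

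**What the plan says.** The Statistical Analysis section describes the primary outcomes as counts of patients: "Statistical comparisons will be made for the number of patients that experience a recurrent or refractory subdural hematoma", and likewise the number who need evacuation surgery after embolization. Each patient either has the event or does not. The section then says "These primary endpoints will be compared with simple t-test". For safety, "the rate of procedure-related complications between embolized patients and surgical controls will be compared by t-test". Neither sentence says whether the variance is pooled or estimated separately by group (Welch), and no confidence-interval method is named. The same section gives the Rankin score a chi-square test.

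Under Methodology, Participants, the plan expects 20% of patients to meet the endpoint without embolization. For the embolized group, "With the addition of MMA embolization, we expect that only 5% of patients will meet this outcome". On size, "we plan to study 200 patients who undergo MMA embolization", compared with 400 historical matched controls, so 1:2 overall. The split of either total between the two aims is not given. Nor is the number of surgical controls, who are the comparator for complications. The controls are called matched, but no matching variables or matched sets are defined.

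**The concern.** For a yes/no outcome the variance is fixed by the event rate, p(1 − p). If the rates differ, the variances differ. A pooled t-test assumes that they are equal, and with groups of unequal size this puts the wrong standard error on the difference. A Welch test avoids that, but it fails in another way when events are rare: a group with no events contributes no variance, so the standard error is too small.

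The plan makes both situations plausible. Its planned rates differ fourfold. Its Risks section cites one series of 60 embolizations and a review of 193 procedures with no procedure-related complications, so an embolized group with no events is possible. At stake are the precision reported for the main effect and the p-value of the safety comparison. Because the form is left open, it could also be chosen after the data are seen.

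**Working it through.** **Inputs.** Event rates of 5% and 20%, and totals of 200 and 400, come from Methodology, Participants. Complication rates come from Prior Research ("2.1% vs 4.4%, OR 0.563", embolization first) and from Risks (9% for burr-hole surgery). The plan prints alpha as 0.5; a two-sided 0.05 is assumed here. The splits 200:200, 100:200 and 100:400 (embolized:controls) are assumptions, used to show a range.

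**The plan's own figure.** The plan says "124 patients will be needed for a power of 80% using a two tailed alpha set at 0.5". The usual formula per arm is n = [z(α/2)·√(2p̄(1 − p̄)) + z(β)·√(p₁(1 − p₁) + p₂(1 − p₂))]² / (p₁ − p₂)², with p̄ = 0.125.
- Alpha 0.05: (1.960 × 0.4677 + 0.842 × 0.4555)² / 0.0225 = 75.1, so 76 per arm and 152 in total.
- Alpha 0.5 as printed: 22 per arm and 44 in total.

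Neither gives 124. The rest of this point does not depend on that figure.

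**Pooled standard error at the planned rates.** The variances are 0.05 × 0.95 = 0.0475 and 0.20 × 0.80 = 0.16, a ratio of 3.4. With 1:2 groups the pooled variance is (0.0475 + 2 × 0.16)/3 = 0.1225.
- 200:400: pooled √(0.1225 × (1/200 + 1/400)) = 0.0303; correct √(0.0475/200 + 0.16/400) = 0.0252; ratio 1.20.
- 100:200: pooled √(0.1225 × 0.015) = 0.0429; correct √(0.0475/100 + 0.16/200) = 0.0357; ratio 1.20.
- Equal groups: ratio 1.00.

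**Coverage, size and power.** These come from exact enumeration. Every pair of event counts is weighted by its two binomial probabilities, the groups are taken as independent, and tables with zero variance count as non-rejections.
- Coverage of the nominal 95% pooled interval at 5% vs 20%: 98.1% (200:400) and 98.2% (100:200).
- Size of the pooled test at 200:400: 4.8% at a common rate of 2.1% and 5.0% at 20%. Pearson chi-square also gives 4.8% at 2.1%.
- Power at 5% vs 20%: 99.98% for both pooled t and chi-square at 200:400; 96.9% and 97.1% at 100:200.

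**Welch false-positive rate on complications,** same enumeration, equal true rates in both groups:

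| Embolized : surgical controls | 2.1% | 4.4% | 9% |
|---|---|---|---|
| 200:200 | 4.5% | 4.9% | 4.8% |
| 200:400 | 5.9% | 5.4% | 5.2% |
| 100:200 | 8.9% | 6.4% | 5.2% |
| 100:400 | 12.6% | 7.3% | 5.7% |

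The rows with 400 are an outer limit, because the 400 controls cover both the medical and the surgical cohort. At a 1% rate, 200:400 gives 8.8%. The excess falls on the side of the smaller group. At 2.1%, the part favouring embolization is 4.6 of 5.9 points at 200:400 and 8.0 of 8.9 at 100:200, but only 1.0 of 8.9 at 200:100.

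**Example: 0/100 vs 4/200.**
- Welch: the control variance is 0.02 × 0.98 × 200/199 = 0.0197 and the embolized group adds nothing. SE = √(0.0197/200) = 0.00992, t = 0.02/0.00992 = 2.02, p = 0.045.
- Pooled: variance 199 × 0.0197/298 = 0.01315, SE = √(0.01315 × 0.015) = 0.0140, t = 1.42, p = 0.16.
- Fisher's exact test: p = 0.31.

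At 0/200 vs 4/400 the three p-values are the same to two figures.

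**The case against.** The best defence is that a simple t-test most naturally means the pooled form. On a 2×2 table that form behaves almost exactly like chi-square under the null, so no false-positive problem arises. The plan specifies no confidence interval, so the 20% excess concerns something that it has not promised. The excess is conservative and leaves power almost unchanged. Welch is not named either, and if 200 embolized patients meet 200 surgical controls it shows no inflation. The complication rate may also be higher than 2.1%: Risks expects access-site hematomas in about 5% of subjects, and the plan does not say whether these count. At a common 5%, Welch gives 4.8% (200:200), 5.4% (200:400) and 6.1% (100:200).

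All of this stands, and it limits the point. A reader might infer that the safety comparison carries about 9% false positives, mostly in favour of embolization. The documents do not support that: it needs the Welch form, a low rate, an unstated group split, and embolization as the smaller group. A reader might also infer that the primary tests are invalid or that a wrong interval is planned. Neither follows.

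What the defence does not remove is that the form is unstated, that the two forms can disagree across the 5% line on the same table, and that neither uses the matching.

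**Conclusion.** The point holds in a conditional form. If the t-test is pooled, its size is sound, and the fault lies in any interval derived from it: 20% too wide at 5% vs 20%, provided that each comparison keeps roughly 1:2. If it is Welch, the false-positive rate on complications runs from 4.5% to 12.6% at a common 2.1% over the splits shown, and from 4.8% to 5.7% at 9%. Which value applies cannot be settled from the documents. These figures assume a two-sided 0.05 and independent groups. The primary conclusions are not threatened at the planned rates. The case for a change is that one loosely named test serves both primary endpoints and the safety comparison, and better-suited methods are readily available.

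**What to change.** In Statistical Analysis, replace the t-tests as follows.
- **Primary endpoints:** report the risk difference with a Newcombe or Miettinen-Nurminen 95% confidence interval. Test with chi-square or logistic regression, adjusted for the matching variables, or conditional on matched sets if such sets are formed.
- **Complications:** report the risk difference in the same way, with Fisher's exact test or Firth logistic regression.
- **Group sizes:** state how many embolized patients and surgical controls enter each comparison.

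No patients, visits or data are added, but the change is not wholly one of wording. An analysis that respects the matching needs the matching variables and method to be defined first. A conditional model also yields an odds ratio, not a risk difference, and drops sets in which all outcomes agree. Fisher's test is somewhat conservative with few events.

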Secondarily, the number of patients in each treatment group that experience persistence or recurrence to the degree that surgical evacuation is required will be compared. Patients who prospectively undergo middle meningeal artery embolization will be compared to retrospective matched controls of patients that underwent medical management. We hypothesize that patients who undergo MMA embolization as compared to simple observation alone will be less likely to ultimately need surgery and have a higher likelihood of SDH resolution after 90 days.

Specific Aim 2:

Determine the safety and efficacy of middle meningeal artery embolization for recurrent and refractory subdural hematomas after initial surgical evacuation.

MMA embolization has emerged as an adjunct treatment for patients who experience recurrent or refractory SDH after initial surgical evacuation. These patients will require surgical evacuation of the hematoma for their condition regardless of the use of MMA embolization. For patients with a residual SDH or who develop recurrent SDH within 30 days of initial standard of care surgery, the patients that have adjunct treatment with MMA embolization will be compared to historical patients that are managed with continued observation versus repeat surgery. We hypothesize that patients who undergo MMA embolization will have a higher likelihood of demonstrating radiographic improvement of the SDH and have a lower rate of requiring additional surgery.

Methodology

Participants

Approximately 200 patients with chronic subdural hematoma are treated at Barnes-Jewish Hospital annually. Patients aged 18+ of any race, sex, and socioeconomic status undergoing treatment for subdural hematoma will be identified by screening of the inpatient neurosurgical units or identification by an investigator. Patients will be approached regarding enrollment in the study at the time a decision is made to treat the subdural hematoma. If a patient expresses interest, an investigator or coordinator will provide the written consent form and explain the

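### The controls are described as matched, but the simple t-test named for both primary endpoints takes no account of matching; if matching is individual and prognostic, that test is conservative

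*Combined protocol and SAP*

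**What the plan says.** Three places describe the controls as matched.

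- Objective, for both embolization groups (the unit, cut off here, is years): "We will compare the outcomes of these two groups of patients who undergo middle meningeal artery embolization to matched historical controls from the past four".
- Specific Aim 1: the embolized patients are to be "compared to retrospective matched controls of patients that underwent medical management".
- Methodology, Participants: "we plan to study 200 patients who undergo MMA embolization", and then "These patients will be compared to an additional 400 historical matched controls obtained via retrospective chart review".

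The sample-size statement in that section, repeated under Safety and Analysis, assumes equal arms and does not mention matching: "With equal numbers of patients in each arm, we estimate that 124 patients will be needed".

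Analysis, Statistical Analysis gives one method for both primary endpoints (recurrent or progressive haematoma, and secondary surgical evacuation): "These primary endpoints will be compared with simple t-test". For safety it adds that "the rate of procedure-related complications between embolized patients and surgical controls will be compared by t-test".

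No paired, stratified, conditional or covariate-adjusted method appears anywhere. The data tables under Privacy/Data Protection have no field linking a patient to a matched set. The matching variables, the algorithm, the number of controls per patient and the choice between individual and frequency matching are not stated. Nor is the division of the 200 and the 400 between the two aims.

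**The concern.** Without randomisation, the comparison rests on the matching. If each embolized patient is matched to particular controls on factors that predict outcome, outcomes within a set tend to agree. An independent-groups variance leaves that covariance out. The estimated difference is unchanged, but its standard error is overstated, so the p-value is too large and any interval built from it is too wide. Perfect balance on the matching variables would not cure this, because it is a question of dependence and not of confounding.

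The precision that matching was meant to buy would be discarded. In a small cohort, a real reduction in recurrence or reoperation could be missed.

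**Working it through.** **Inputs from the documents.** Event rates 20% (controls) and 5% (embolization); power 80%; two-tailed test; 200 embolized and 400 controls. **Assumptions.** Two-sided alpha 0.05 (the protocol prints 0.5); one embolized patient and two controls per set; within-set correlation ρ from 0 to 0.3. The largest correlation attainable between a 5% and a 20% binary outcome is (0.05 − 0.05×0.20)/√(0.0475×0.16) = 0.46.

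**1. The plan's own figure.** For unmatched equal arms, n per arm = [1.96√(2×0.125×0.875) + 0.842√(0.20×0.80 + 0.05×0.95)]²/0.15² = 1.300²/0.0225 ≈ 75.1, so 76 per arm and 152 in total. The stated 124 is not reproduced: 62 per arm gives 71.9% power, and alpha 0.5 as printed gives 44 in total. That is a separate matter; here it shows only that the standard unmatched formula does not yield 124.

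**2. Variance with and without the sets.** For one embolized patient minus the mean of two controls:

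- independent groups: p₁q₁ + p₂q₂/2
- matched sets: p₁q₁ + (p₂q₂/2)(1+ρ) − 2ρ√(p₁q₁p₂q₂)

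With equal rates, the second reduces to 1.5pq(1−ρ). The independent standard error is then too large by the factor 1/√(1−ρ), and the true two-sided error rate is 2Φ(−1.96/√(1−ρ)). The simulated column gives the range over repeated runs, with a shared set effect on the logit scale, 200:400 and 20% in both groups.

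| ρ | SE factor | False-positive rate, formula | False-positive rate, simulated |
|---|---|---|---|
| 0 | 1.00 | 5.0% | – |
| 0.05 | 1.03 | 4.4% | 4.1–4.5% |
| 0.2 | 1.12 | 2.8% | 2.7–2.8% |
| 0.3 | 1.20 | 1.9% | 1.9–2.1% |

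Set-based tests stayed at about 5% throughout.

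At the planned 5% versus 20%, the independent variance is 0.0475 + 0.08 = 0.1275. At ρ = 0.2 the matched variance is 0.0475 + 0.096 − 0.0349 = 0.1086, and √(0.1275/0.1086) = 1.08. At ρ = 0.05 and 0.3 the ratios are 1.02 and 1.13.

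**3. Power at 5% versus 20%, planned sizes.** At 200:400 the independent standard error is √(0.1275/200) = 0.0252, and 0.15/0.0252 is about 5.9, so power exceeds 99.9% with either analysis. At 100:200 (an assumed even split between aims), simulated power for the pooled t-test against the set-stratified Mantel-Haenszel test is 97.7% against 98.5% at ρ = 0.2, and 98.1% against 99.2% at ρ = 0.3.

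**4. Where power does move (simulated).**

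| Setting | ρ | Pooled t | Welch t | Mantel-Haenszel by set |
|---|---|---|---|---|
| 50:100, 5% vs 20% | 0.2 | 76% | 85% | 81% |
| 50:100, 5% vs 20% | 0.3 | 77% | 86% | 85–86% |
| 100:200, 10% vs 20% | 0.2 | 61–62% | 68% | 70% |
| 100:200, 10% vs 20% | 0.3 | 61–62% | 68% | 75–76% |
| 62 pairs, 5% vs 20% | 0.3 | 77–78% | same (equal arms) | 83% |

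The 50:100 split and the 10% rate are illustrations; neither is in the documents. At 50:100 the conditional-type test is weaker than Welch up to ρ of about 0.2 (75% against 84% at ρ = 0.05). A risk difference with set-clustered standard errors stays within about 2 points of Welch at low ρ and passes it from about 0.2.

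**The case against.** A reader might infer that two controls are tied to each embolized patient and that the standard errors are simply wrong. The documents do not support this. Two per patient is only the ratio 400/200. The list of groups names two historical cohorts, medical management and surgery alone, so 400 could be 200 in each or a frequency-matched pool with no sets at all.

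The direction is also conditional. The effect is nil at zero correlation. If only the two controls in a set correlated with each other (0.05 to 0.3), the independent standard error would be about 1.5% to 8% too small. A correlation of 0.2 to 0.3 is demanding: the matching variables would have to predict the outcome with an area under the curve of roughly 0.79 to 0.85 and be matched perfectly.

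The error is conservative, so it produces no false claim of benefit. Part of the apparent power gap at 50:100 comes from assuming the pooled form of the t-test, which the protocol does not specify.

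All of this stands, and it limits the point. It does not remove it. The controls are called matched, and the only named test ignores matching whether it is individual or by frequency. Reading that test as independent-groups is an inference, but a natural one: the text compares numbers of patients in each group and mentions no pairing.

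**Conclusion.** The mismatch between a matched design and the named primary analysis is real. Its consequence is conditional. With individual 1:2 matching, positive within-set correlation and two-sided alpha 0.05, a nominal 5% test with 20% event rates in both groups runs at about 4% (ρ = 0.05), 2.8% (0.2) or 2.0% (0.3), and its standard errors are correspondingly too large.

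Two stronger readings should be resisted. One is that the study loses power as planned: at 5% versus 20% it does not, at 200:400 or at 100:200. A loss needs a smaller cohort or a smaller true effect, together with a correlation of about 0.2 or more. The other is that the complication comparison suffers in the same way. It uses surgical controls, whereas Aim 1 patients are matched to medically managed ones and would have no surgical set-mate, so the point reaches only embolized patients who have matched surgical controls.

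**What to change.** In Statistical Analysis, replace the simple t-test for both primary endpoints, separately for Aim 1 and Aim 2, with a risk difference and 95% confidence interval that account for the matching. State the matching variables, the ratio and whether matching is individual or by frequency.

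- **Individual matching:** record a matched-set identifier when controls are selected and use set-clustered (robust) standard errors. Keep conditional logistic regression as a supporting analysis only, because concordant sets contribute nothing to it and it loses power.
- **Frequency matching:** there are no sets, so adjust for the matching factors.
- **Complications:** apply the same approach only to embolized patients who have matched surgical controls.

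The cost is a short change to the analysis text and, for individual matching, one database column; no extra patients or procedures. The identifier should be captured at selection because it may be hard to reconstruct later. If the matching factors prove unrelated to outcome, power falls by up to about 2 points (for example 75% to 73% with 62 pairs).
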